#### A) PROJECT SUMMARY

Over five million Americans have Alzheimer's disease (AD), and this number is expected to triple by 2050 unless effective preventive strategies are identified. Veterans are at an even higher risk for AD than the general population, possibly due to their increased exposure to factors that accelerate AD pathology, including vascular risk factors, traumatic brain injury, and posttraumatic stress disorder. AD pathology occurs decades before cognitive symptoms occur and is characterized by amyloid plagues, neurofibrillary tangles, and reduced regional cerebral blood flow in areas of the brain related to memory and learning. While cerebral arterial dysfunction occurs early in the development of AD pathology and decades before symptoms begin, the effects of treating such early vascular dysfunction in the brain are poorly understood. The omega-3 fatty acid eicosapentaenoic acid (EPA) improves arterial function and cerebral blood flow, attenuates adverse brain changes related to β-amyloid protein, and improves cognition in animals – changes that could all potentially protect against AD. However, it is not clear whether EPA beneficially affects these processes or cognitive performance in cognitively-healthy adults at increased risk for AD. In 2012, the Food and Drug Administration approved the first high-dose prescription EPAonly medication to treat hypertriglyceridemia, called icosapent ethyl (available as Vascepa® in the United States). This agent is readily available for use and has a good safety profile, making it a favorable agent to consider for AD prevention.

The proposed study is a proof-of-concept, randomized, placebo-controlled, double-blind, parallel-group clinical trial assessing the efficacy of 18 months of icosapent ethyl (IPE) therapy on magnetic resonance imaging (MRI), cerebrospinal fluid (CSF), and cognitive biomarkers for AD in 150 cognitively-healthy Veterans ages 50–75 years. Since Vascepa® has a daily dose recommendation of 4 grams daily, participants will be randomized to either 4 gram daily IPE (Vascepa®) or matching placebo. The overarching goal of this trial is to assess whether IPE beneficially affects intermediate physiological measures associated with the onset of AD in order to evaluate whether larger, multi-site, longer-duration Alzheimer's prevention trials are warranted to assess more definitive clinical outcomes.

### B) BACKGROUND AND SIGNIFICANCE

AD is a devastating illness leading to progressive neurodegenerative changes and cognitive decline. Current therapies to treat AD are limited in their efficacy and work primarily to delay the inevitable decline in function. Disease-modifying and preventive therapies have not yet been identified. The projected tripling of the number of persons with AD in the United States in the next 40 years has led to an urgent need to rapidly identify AD preventive strategies. Veterans are at even higher risk of developing AD than the general population due to a variety of factors including increased prevalence of vascular risk factors, traumatic brain injury (TBI), post-traumatic stress disorder (PTSD), and depression. While longitudinal studies such as the groundbreaking Department of Defense Alzheimer's Disease Neuroimaging Initiative (DOD-ADNI) are seeking to better understand how TBI, PTSD, and depression contribute to AD pathology in Vietnam Veterans, some earlier data suggest that these conditions may mediate AD risk in part through vascular mechanisms. Depression and AD both share common vascular risk factors and Veterans treated for PTSD are more than twice as likely to have dyslipidemia or hypertension compared to Veterans without PTSD. Within the Veteran population, persons who are eligible for and use care through the Veterans Affairs (VA) system have an even greater risk for AD than non-VA Veterans due to their aggregation of risk factors related to VA eligibility - on average, they have lower income, are less likely to be employed, have fewer years of education, and are more likely to have

service-related medical or psychiatric conditions. In addition, compared to non-VA Veterans, VA Veterans are more likely to be African American – a population with increased incidence rates of vascular risk factors and twice the prevalence of AD compared to white adults. Based on available data, experts anticipate 423,000 new cases of AD in Veterans by 2020, including 140,000 cases directly attributable to military service. Thus, finding effective therapies to prevent or delay the onset of AD in Veterans is critical. The VA is poised to lead cutting-edge AD prevention research that includes Americans with a high likelihood of developing AD – namely Veterans within the VA healthcare system.

Evidence supports that AD neurodegenerative changes likely begin decades before clinically-apparent disease. The NIA-Alzheimer's Association (AA)-sponsored workgroup defined research criteria for the preclinical stages of AD and identified factors that best predict risk of progression from "normal" cognition to mild cognitive impairment (MCI) and AD. Our investigative team at the NIH-funded, jointly-sponsored University of Wisconsin (UW)/ Madison VA Wisconsin Alzheimer's Disease Research Center (ADRC) has focused our studies on early identification and treatment of such preclinical, high-risk individuals - in particular, asymptomatic middle-aged adults with parental history of AD. While previous studies have demonstrated that having a firstdegree relative with AD increases the risk of developing AD, independent of the risk conveyed through the genetic risk factor apolipoprotein Ε ε4 (APOE4) allele, more recent research supports that biomarker elevations, but not APOE or parental history status, are associated with risk of cognitive decline in cognitively unimpaired adults. 1 Our Wisconsin ADRC investigators have found that asymptomatic middle-aged adults with parental history of AD show early neurobiological changes on CSF biomarkers, MRI biomarkers including measures of regional cerebral blood flow (rCBF), and cognitive biomarkers for AD while demonstrating normal global cognitive and clinical function. In a group of 218 cognitively healthy adults ages 40-65 years with parental history of AD in our Wisconsin ADRC-related studies, we found that 129 (60%) are either carriers of the APOE4 allele or have CSF β-amyloid-42 (Aβ42) or tau biomarker levels suggesting preclinical disease (preliminary data, unpublished). Thus, these high-risk individuals are ideal to study in that they are clinically asymptomatic, yet have neurobiological evidence supporting preclinical AD-related changes in their brains. For the proposed clinical trial, we will focus on cognitively healthy Veterans ages 50-75 years with or without parental history of AD. Participants will have Veteranspecific risk factors related to increased prevalence of atherogenic vascular risk profiles, TBI, PTSD, and depression. In addition, we will gather information on their parental history of AD to account for potential risk variation given the conflicting findings on the importance of parental history of AD in the development of this common form of dementia.

#### **Hypothesis:**

In middle-aged and older cognitively-healthy Veterans (ages 50–75), 18 months of treatment with icosapent ethyl (IPE) will beneficially modify preclinical AD biomarkers, including regional cerebral blood flow (rCBF), cerebrospinal fluid (CSF) markers of AD pathology, and cognitive performance.

#### **Specific Aims:**

- (a) To investigate the effects of 18 months of IPE 4 g daily vs. placebo on arterial spin-labeling (ASL) MRI regional cerebral blood flow (rCBF) in a pre-defined statistically-identified region of interest (ROI) affected early in preclinical AD.
- **(b)** To determine the impact of 18 months of IPE vs. placebo on CSF biomarkers of preclinical AD pathology (CSF  $\beta$ -amyloid-42, total tau, and phosphorylated tau181).

**(c)** To evaluate the effects of 18 months of icosapent ethyl vs. placebo on a composite measure designed to assess preclinical cognitive changes — the Alzheimer's Disease Cooperative Study (ADCS) Preclinical Alzheimer's Cognitive Composite (PACC).

Description of the primary endpoint: The primary endpoint will be the change in rCBF in a predefined statistical ROI at 18 months in participants randomized to IPE vs. placebo. Animal and human studies show that regionally reduced CBF (related to both neuronal hypometabolism and systemic vascular disease) in areas of the brain important for memory and learning is a very early change in AD pathogenesis and, thus, therapies known to beneficially modify arterial function may improve CBF and lead to early neuroprotection and maintenance of cognitive function. The predefined statistical ROI that will be used for the proposed trial was developed using longitudinal ASL-MRI CBF data from 133 adults (ages 43-73) in the NIH-funded Wisconsin Registry for Alzheimer's Prevention (WRAP) cohort, which is enriched for parental history of AD. Areas of the brain with greatest CBF decline over two years were identified using the Alzheimer's Disease Neuroimaging Initiative (ADNI)-derived analytic method developed by Chen et al. The statisticallydefined region is consistent with those affected early by AD pathology. Using anatomical ROIs that aligned with the statistically-defined ROI, treatment effect on 18 month rCBF was examined hierarchically in a priori selected regions of interest in the following order: bilateral posterior cingulate, bilateral precuneus, bilateral medial temporal lobe. Analyses of ROIs were discontinued if the group difference in 18 month rCBF in the previous ROI was not significant. Secondary endpoints will be 18-month changes in CSF biomarkers of AD pathology (Aβ42, t-tau, p-tau) and changes in ADCS-PACC cognitive score.

If IPE beneficially modifies AD biomarkers in at-risk Veterans, the results from the proposed trial would be used to develop multi-site, longer-duration clinical trials using the VA Cooperative Studies Program to assess the efficacy of icosapent ethyl on not only AD biomarkers, but also on more clinically definitive outcomes, such as rate of cognitive decline and conversion to mild cognitive impairment (MCI). If future studies show that icosapent ethyl delays the onset of AD by even an average of 5 years, estimates suggest that this could reduce the prevalence of AD by about 50%.

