To test this hypothesis, we will enroll 150 cognitively healthy male and female Veterans and randomize them in a 1:1 ratio to IPE 4 g daily or matching placebo. All participants will undergo informed consent and will be screened for eligibility via a pre-study screening visit (Table 2). At baseline and months 9 and 18, all participants will undergo MRI, lumbar puncture (LP) for CSF collection, a blood draw, cognitive testing, vascular risk assessment, and will complete questionnaires including a food frequency questionnaire (FFQ) targeting omega-3 fatty acid intake and screening questions assessing prior combat and non-combat deployment, TBI, PTSD, and related sequelae. At months 1, 3, 6, 12, and 15, participants will have an assessment of medical/medication changes and potential side effects, interim lab assessments as indicated (aspartate transaminase [AST], alanine transaminase [ALT], urine pregnancy as needed) (Table 2), have vitals and body measurements collected, and be evaluated for depression using the Hamilton Rating Scale for Depression (HAM-D) test. As detailed in the Statistical Analysis section, using a two-sided test at the 0.05 level and anticipating a conservative 90% retention rate, a sample size of 150 participants will provide 90% power to detect significant changes in our primary and key secondary outcomes. Specifics of the above procedures are outlined below.

We will aim to schedule study visits within 8 weeks of the target visit time, but it is possible that the actual visit will be outside of this window. If the final visit is delayed, we may ask the participant to remain on the study medication for no more than 6 additional months based on statistical analysis, resources, funding, or other factors. This will ensure the study team to collect accurate results at the participant's final biomarker visit.

If the participant does not bring their remaining study medication to their final visit, we will provide them with a postage-paid envelope to return the medication to the study team for disposal. If this envelope was not provided at the visit, it will be sent with a letter requesting the return of the study medication. If we do not receive the remaining study medication, the study team will create a note to file documenting that the participant completed the study, but any remaining study medication was not returned.

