#### **Analyses**

For imaging analyses, the statistical models prescribed by our ADRC biostatistician can be effected in SPM (including SPM5, SPM8, and SPM12) or AFNI. Analyses will use an empirically predefined statistical region of interest (sROI) to characterize the treatment effect with optimal power and freedom from multiple comparisons as described by Chen and Reiman. The sROI was defined using a training dataset, i.e., an independent longitudinal dataset (baseline and follow-up without treatment) of ASL-CBF maps collected in asymptomatic, middle-aged adults with a parental history of AD. Using a paired-samples voxel-wise t-test in SPM, the training dataset was analyzed for regions of statistically significant CBF declines. The candidate regions for the sROI were selected based on those that best characterized CBF declines in this group in regions implicated in AD pathology. The sROI will then be applied to ASL-CBF maps in the current study, and averaged values from the sROI will be extracted for statistical analysis. The predefined sROI facilitates correction for multiple comparisons and reduces our exposure to Type 1 error by greatly

reducing the number of voxels in the search region that are evaluated. Anatomical ROIs that aligned with the statistically-defined ROI will be examined hierarchically in a priori selected regions of interest in the following order: bilateral posterior cingulate, bilateral precuneus, bilateral medial temporal lobe. Analyses of ROIs will be discontinued if the group difference in 18 month rCBF in the previous ROI is not significant.

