#### **Power Calculations**

For Aim 1, using ASL-MRI CBF data from our team's longitudinal WRAP cohort of adults at risk for AD (n=133, ages 43–73) and an interventional statin pilot study of similarly aged adults,16 we anticipate that CBF in the statistical ROI will decline by 15% in the placebo group and 5% in the treatment group over 18 months. With an effect size of 0.57 and a two-tailed  $\alpha$ =0.05, 134 participants (67 per arm) will provide 90% power (1- $\beta$ ) to detect a difference between the two treatment groups. With a conservative 10% drop-out rate (our prior 9-18-month studies with n=88–100 had 94–95% retention rates), 150 participants (presumed 134 [90%] retained at month 18) should provide 90% power to detect a statistically significant difference. Using our team's preliminary baseline data from the SHARP study (Table 1), for Aim 2 we use a baseline CSF A $\beta$ 42 mean  $\pm$  SD of 778.2 $\pm$ 173.2 ng/L (INNOTEST) and a projected IPE-induced decline of approximately 13% in the treatment group and 0% in the placebo group over 18 months. With an effect size of 0.59 and a two-tailed  $\alpha$ =0.05, 124 participants (62 per arm) will provide 90% power (1- $\beta$ ) to detect group differences in CSF biomarkers. As the ADCS-PACC battery (Aim 3) has been principally used in cognitively-healthy, preclinical older adults in their 70s-80s, Aim 3 will be used to understand the performance of this established preclinical cognitive battery in a middle-

aged cohort and to correlate cognitive changes with those noted in primary MRI and CSF biomarker changes.

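### The anatomical-region gate stops the analysis of later regions, not only the significance claim, so precuneus and medial temporal effects may go unestimated without any gain in error control

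*Combined protocol and SAP*

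**What the plan says.** The primary endpoint is rCBF in a statistically defined region of interest (sROI). Under the Specific Aims heading, the description of the primary endpoint adds a chain of anatomical regions that align with the sROI, taken in a fixed order, and then: "Analyses of ROIs were discontinued if the group difference in 18 month rCBF in the previous ROI was not significant". The Analyses section repeats the rule in the future tense, "Analyses of ROIs will be discontinued if the group difference in 18 month rCBF in the previous ROI is not significant", and gives the order as "bilateral posterior cingulate, bilateral precuneus, bilateral medial temporal lobe".

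The same section specifies the model for Aim 1: an ANCOVA on the log scale with 18-month sROI rCBF as outcome, treatment as a factor and baseline rCBF as a covariate. No model is written for the individual anatomical regions. The exploratory imaging measures listed in the Trial Design Summary do not name regional CBF. The sROI analysis itself is not described as gated.

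On purpose, the Project Summary says: "The overarching goal of this trial is to assess whether IPE beneficially affects intermediate physiological measures associated with the onset of AD". It adds that this is meant to show whether larger and longer prevention trials are justified.

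**The concern.** A fixed-sequence procedure controls the family-wise error rate by forbidding confirmatory claims after the first non-significant step. It places no restriction on estimating the remaining effects and showing them as descriptive results. The plan's wording goes further. Under it, a posterior cingulate p-value of 0.06 would mean that no treatment difference is computed for the precuneus or medial temporal lobe, although both were chosen in advance and the images are already acquired.

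There is a second, smaller effect. If the regional estimates are positively correlated, later regions are analysed mainly in trials where an earlier estimate happened to be high. The later estimates are then, on average, too high.

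What is at stake is regional information for planning a follow-on trial. The sROI value is an average over its territory, so it cannot show where in that territory an effect lies.

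**Working it through.** **Inputs from the documents**
- Two-sided 0.05 (Trial Design Summary: "using a two-sided test at the 0.05 level"). No separate level is given for the regional chain, so 0.05 is used at each step.
- Effect size 0.57 SD, stated for the sROI (Power Calculations: "With an effect size of 0.57 and a two-tailed"), from the expectation that "CBF in the statistical ROI will decline by 15% in the placebo group and 5% in the treatment group over 18 months".
- 67 evaluable per arm ("134 participants (67 per arm) will provide 90% power").

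**Assumptions, because the documents are silent**
- The true effect in each anatomical region: 0.57 SD in all three (the sROI figure carried over), then 0.30 SD in all three.
- The correlation rho between regional estimates, taken as equal for each pair: 0 to 0.9.

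**Step 1. Reproduce the plan's own figure.** The standard error of a standardised difference is sqrt(2/67) = 0.173. Then 0.57/0.173 = 3.30, and power = Phi(3.30 - 1.96) = 0.91. The required number per arm is 2 x ((1.96 + 1.28)/0.57)^2 = 64.7, so 65, or 66 with a t-test, against 67 stated. With 10% dropout, 134/0.90 = 148.9, so 149 against 150 stated. The plan's figures hold.

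**Step 2. Probability that the precuneus is never analysed.** This is the probability that the posterior cingulate is not significant, and it does not depend on rho.
- 0.57 SD: 1 - 0.91 = 9%.
- 0.30 SD: 0.30/0.173 = 1.74. Power is Phi(1.74 - 1.96) plus a negligible opposite tail, about 0.41, so 59%.

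**Step 3. Medial temporal lobe.** It is reached only if both earlier regions are significant. Three estimates with standard error 0.173 and common correlation rho were simulated (2,000,000 trials per setting).

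| True effect, all regions | rho | No precuneus estimate | No medial temporal estimate | Mean medial temporal estimate when reached |
|---|---|---|---|---|
| 0.57 SD | 0 | 9% | 17% | 0.57 |
| 0.57 SD | 0.5 | 9% | 15% | 0.60 |
| 0.57 SD | 0.9 | 9% | 12% | 0.61 |
| 0.30 SD | 0.3 | 59% | 78% | 0.38 |
| 0.30 SD | 0.5 | 59% | 75% | 0.42 |
| 0.30 SD | 0.7 | 59% | 71% | 0.45 |

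At 0.57 SD the average inflation of the medial temporal estimate is therefore 0% (rho 0) to 6% (rho 0.9). At 0.30 SD it is 0.38/0.30 to 0.45/0.30, or roughly 27% to 50%, for rho 0.3 to 0.7. At rho = 0 there is none, whatever the effect.

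**Step 4. After the change.** If all three regions are always estimated, each estimate is available in every trial and averages the true effect. The 95% interval has a half-width of about 1.96 x 0.173 = 0.34 SD. The first test in the chain is still at 5% and claims still stop at the first failure, so the family-wise error within the chain stays at 5%.

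**The case against.** Four points can be made on the other side.

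- **The wording may be shorthand.** Describing fixed-sequence testing as examining regions hierarchically and stopping is common, and nothing in the documents forbids descriptive reporting of later regions. This is fair, but nothing provides for it either. The Aim 1 ANCOVA is for the sROI, and the general commitment to statistical graphics guarantees no regional estimate. If shorthand was meant, the proposed sentence simply records the intent.
- **The large figures need unfavourable assumptions.** This stands. The only rCBF effect size in the documents is 0.57, and there the loss is modest. The 0.30 SD scenario is illustrative. An effect that grows along the chain, against the chosen order, would look worse still, but no section supports that pattern.
- **The ungated sROI result informs the decision on further trials.** This also stands. A reader might infer that the trial's proof-of-concept purpose fails without an estimate for each region. The Project Summary does not say so, and the sROI estimate covers the aligned territory. What is lost is information about location within it.
- **The gate is a valid test.** Agreed. The order is fixed in advance, and nothing here questions the error control within the chain.

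A reader might also infer that later regions are reported only in trials where their estimates are inflated. That does not follow. Inflation is an average over trials that pass the gate. At 0.57 SD and rho 0.5, about 44% of the medial temporal estimates that are reached lie below the true value; at 0.30 SD and rho 0.5, about 21% do.

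**Conclusion.** The concern holds as one of estimation and reporting. Both statements of the rule stop the analysis, no other section supplies the missing estimates, and stopping the analysis adds nothing to the error control that stopping the claims already gives.

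The size depends on regional effects that the documents do not state. If the planned 0.57 SD applied in every region, the loss would be modest and the inflation slight. It becomes serious only if the true regional effects are well below plan; marked inflation also needs correlated regions, which is plausible for neighbouring areas but undocumented. The loss of estimates needs no correlation at all.

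The sROI primary analysis, the sample size and the stated power are untouched. The documents do not support a reading in which the primary result is compromised or the regional estimates are always biased. This should be changed because the change is nearly free, not because the trial's main conclusion depends on it.

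**What to change.** In both places, the primary endpoint description under Specific Aims and the Analyses section, replace the discontinuation sentence with text to this effect:

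*Formal significance claims stop at the first anatomical ROI that is not significant. The baseline-adjusted treatment difference, from the Aim 1 form of ANCOVA on the log scale with that ROI's own baseline value, and its 95% confidence interval are reported for all three ROIs whatever the result of the sequence. Results beyond the stopping point are labelled descriptive.*

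The cost is one sentence in each place and at most two further fits of the same model on scans already acquired. The past tense under Specific Aims is no obstacle: if the sequence has already been run, the remaining models can still be fitted and shown as descriptive.
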